5.8 Withdrawal of Subjects

Participants who wish to withdraw may do so at any time without affecting their medical care or participation in any other study. Participants will be informed of any new information throughout the duration of the study which may affect their condition or influence their willingness to continue in this study. Finally, based on decisions made by the Principal Investigator, participants may be taken out of the study because of unanticipated circumstances such as extreme distress. That is, they may be withdrawn from the study if we judge that participating is not in their best interest.

6.0 Protection of Human Subjects

Protection of Human Subjects

Risk to Participants

Human Subjects Involvement and Characteristics. The purpose of the study is to test the effects of Cognitive-Behavioral Therapy for Treatment Seeking (CBT-TS) CBT-TS in increasing the initiation of psychosocial pain treatment among Veterans using opioid analgesics for chronic pain. Secondary goals are to assess the effects of CBT-TS on treatment retention and its downstream effects on pain and opioid use outcomes. We will also explore CBT-TS effects on treatment engagement of other non-pharmacological pain treatments and mechanisms of change to identify barriers to engagement in non-pharmacological pain treatment. A total of 300 veterans will be recruited nationally and randomized to receive either CBT-TS (n = 150) or an Education control (n = 150). Over 50% of Veterans in the Veterans Health Administration (VHA) have received a diagnosis of a musculoskeletal condition (the majority of which are associated with chronic pain) between 2000 and 2011. Of these individuals, over one-third are over 65 years of age, nearly three-quarters are White and fewer than 10% are women. Hypertension occurs in approximately half of these Veterans and other medical conditions including diabetes, coronary artery disease, and chronic obstructive pulmonary disease occur in over 10% of Veterans with a musculoskeletal condition. We expect to have a greater proportion of women and racial/ethnic minorities relative to the above as we will target them in recruitment.

Inclusion criteria: Participants will include men and women Veterans who:

- Are English-speaking
- Are 18 years of age or older
- Are taking at least 20 mg morphine equivalent daily dose of opioid analgesics per day for ≥ 90 days
- Pain that occurs on at least half the days for 6 months or more
- Score ≥ 4 on each of the three items of the PEG
- Optional Add-on Study: Identify as African American

Exclusion: Veterans will be excluded on the basis of:

- Used a nonpharmacological approach to pain management in the last 30 days
- Has cognitive impairment
- Being in hospice, undergoing oncology treatment, or has a recent or upcoming surgery

Pregnant women will not be excluded from this study as no invasive medical procedures are being performed and there is no known risk to the mother or the fetus of the proposed interventions. The study will not include prisoners or institutionalized veterans.

Source of Materials. Study materials will include self-report questionnaires. The materials will be collected for study purposes only. Information collected will be stored in a locked filing cabinet in a locked office at the study sites that can only be accessed by members of the study team. *All electronic data* will be stored on VA Informatics and Computing Infrastructure (VINCI) project servers. Only approved study team personnel who will be involved in data entry, management and analyses will be granted access to this data. All computers are password protected.

Potential risks.

Psychological distress. Anticipated risks to the participants from assessment procedures and therapy are minimal; however, participants may experience psychological distress, frustration, and/or fatigue. The semi-structured interviews, assessments associated with the intervention, and therapy sessions encourage participants to recall personal events and life stressors that

may evoke distress. Additionally, confidentiality may need to be breached if a participant poses a threat to him or herself or others, including child abuse.

Adequacy of Protection from Risk Recruitment and Informed Consent.

All research staff conducting recruitment and informed consent will have completed appropriate and up-to-date training in research, research ethics and the proper conduct of research that includes common issues related to recruitment and informed consent.

Veterans will be identified using structured queries of VA administrative datasets. Research staff will use these lists to identify potentially eligible participants and to enhance the number of Veterans at high risk, women and/or minorities recruited into the study. Research staff will mail an IRB-approved letter describing the study to the Veteran. Research staff will call all patients who receive a letter unless the patients call a number to opt out. These are Syracuse VA IRB-approved procedures that are used by researchers at the Center of Excellence for Suicide Prevention and Syracuse VAMC. There is no more than minimal risk to the participants and the rights of the participants, or their welfare, will not be adversely affected. Recruitment and informed consent procedures were designed to ensure patients do not feel like participation is required. Patients unable to understand the informed consent process will be excluded from participating. Screening interviews will be completed initially over the telephone (using a script) to assess eligibility criteria. Verbal consent will be obtained at this time to complete the screening. Participants screening positive for exclusion criteria will not be included in the study. Veterans who report suicidal intent with a plan will be transferred to the Veteran's Crisis Line (as detailed below in Protection Against Risk). For eligible and interested participants, a research assistant will review the consent form and complete a brief questionnaire to ensure the potential participant understands the study.

Participants will receive compensation for their participation in the study. The compensation amount will be based on the schedule that follows:

Baseline Assessment	\$50
1-month Assessment	\$40
3-month Assessment	\$40
6-month Assessment	\$40

Therefore, the total compensation for completing all the study components would be \$170. Payments will be made following each study procedure listed above. Participants who do not complete the entire study for any reason, will receive compensation for the components that were completed per the above schedule of payments.

Optional Add-on Study: In addition to the compensation provided for participation in the parent project, participants who consent to participate in this add-on project will receive additional compensation for their participation. The compensation amount will be based on the schedule that follows:

Baseline Assessment	\$50
1-month Assessment	\$50
3-month Assessment	\$50
6-month Assessment	\$50

Therefore, the total compensation for completing all the study components for the add-on study would be \$200 (Grand total of \$370, including the \$170 received for participation in the parent study). Payments will be made following each study procedure listed above. Participants who do not complete the entire study for any reason, will receive compensation for the components that were completed per the above schedule of payments.

Protection Against Risk.

Psychological distress. The potential risks are negligible. There are no known risks associated with interview procedures. Participants will be informed that they may feel slightly uncomfortable discussing some of their symptoms. Mild discomfort may occur during the intervention session; however, this is unlikely to have a serious negative impact on the participant's well-being. Participants will be told they can withdraw from the study at any time. Participation or withdrawal from the study will not affect any benefits to which they are otherwise entitled. Special precaution will be taken to safeguard confidentiality. During assessments, if the interviewer is concerned about thoughts and planning of a suicide attempt, the interviewer will ask two follow-up questions: Do you have a desire to kill yourself that you think you might act on and Do you have a plan for killing yourself and intend to carry the plan out? With this information and available suicide assessment measures, the interviewer will evaluate the severity of the participant's suicide risk. If the participant is deemed to be at imminent risk, a safety plan will be initiated. All study staff will receive adequate training in suicidal ideation and risk assessment, and all work will be supervised by Drs. [name] or [name], who are licensed clinicians.

Psychological distress. The potential risks are negligible. There are no known risks associated with interview procedures. Participants will be informed that they may feel slightly uncomfortable discussing some of their symptoms. Mild discomfort may be likely during the intervention session; however, this is unlikely to have a serious negative impact on the participant's well-being. Participants will be told they can withdraw from the study at any time. Participation or withdrawal from the study will not affect any benefits to which they are otherwise entitled. Special precaution will be taken to safeguard confidentiality. During assessments, if the interviewer is concerned about thoughts and planning of a suicide attempt, the interviewer will ask two follow-up questions: Do you have a desire to kill yourself that you think you might act on and Do you have a plan for killing yourself and intend to carry the plan out? With this information and available suicide assessment measures, the interviewer will evaluate the severity of the participant's suicide risk. If the participant is deemed to be at imminent risk, a safety plan will be initiated. All study staff will receive adequate training in suicidal ideation and risk assessment, and all work will be supervised by Drs. [name] or [name].

All assessors and interventionists will have a specific protocol to follow regarding emergency care and will have the clinical back-up of [name] and [name]. This study will use safety procedures that have been previously approved by the IRB in several of our protocols. All research staff will be thoroughly trained on these procedures. These include written procedures for handling emergencies, a written procedure for conducting a full suicide risk assessment whenever suicidality is endorsed, procedures for participants endorsing a suicidal plan or intent (including staying with a patient until they are connected with a mental health provider or 911 help), and a written warm-handoff guideline to connect Veterans to the National Veterans/Military Crisis Line (VCL).

Besides responses on study assessment instruments, participants may also allude to suicide or make other provocative statements, irrespective of the scale rating, and in these instances the research assistant may also decide to transfer the participant to the VCL. A participant's

answers to other questions in the research battery may also persuade the research assistant to transfer the participant to the VCL, irrespective of the scale rating.

For example, a participant may score in the severe depression range on the PHQ-9 depression scale and, together with other information obtained during the call, the research assistant may perceive acute risk and decide to transfer the participant to the VCL.

In any of the above instances, the research staff member will read (or paraphrase) the following statement to the participant at the end of the call:

I am concerned about your safety and so at this time I am going to transfer you to speak with one of our mental health clinicians at the Veterans/Military Crisis Line. There will be a moment of silence as I connect you. If for some reason we get disconnected please dial [name] and press #1 to reach the Lifeline. I will stay on the line with you until the transfer is complete. I am now going to transfer you. Please stay on the line.

The researcher will briefly summarize the participant's situation to orient the VCL responder to the nature of the call (the participant will hear a moment of silence at this time, and then the participant will be transferred to the VCL.

If the participant hangs up or becomes disconnected, the researcher will call the VCL immediately, and the VCL staff will take necessary actions as appropriate according to the VCL safety protocol and/or direct the researcher what actions to take. These actions may include initiating a "rescue" that involves calling 911 at the participant's local jurisdiction and having emergency personnel come to the participant's home to ensure their safety. The VCL staff performs rescues every day, and all rescues are done in collaboration with a supervisor. We have ongoing collaborations with the VCL and have substantial experience working with responders and supervisors. Our approach to participant safety will be applied to all participants including control participants and is guided by ongoing clinical and research experience in suicide prevention, including our Center Director's affiliation with the VCL.

We will collaborate closely with the VCL during the study start-up phase to review these safety protocol steps. As a reminder, the VCL, which was established in 2007 at the Canandaigua VAMC, can be reached anytime by calling [name]. The VCL has grown to be one of the largest in the world, with a full-time staff of more than 600 full-time responders. VCL responders are paid professional staff and nearly all have a Master's degree in a relevant field (e.g., mental health counseling), distinguishing the VCL from others in the U.S. that are staffed primarily with volunteers.

VCL resources will be available as back-up at all times during study sessions. VCL responders are arguably the foremost experts in managing acute suicidal crises via telephone. They have in place protocols for locating suicidal individuals, identifying the closest police and emergency medical services, and monitoring and documenting "rescues." Moreover, VCL responders have the ability to look up call histories based on callers' phone numbers, a capability that since implemented has greatly aided the ability of responders to rapidly assess callers' needs.

All participants will be provided the VCL phone number at the end of each baseline assessment and at each follow-up assessment and encouraged to call the number should they become suicidal, simply wish to talk with someone, or would like assistance in obtaining a referral for mental health treatment. In situations in which potential suicide risk is identified during a phone call, we plan to use two levels of response: 1) researcher transfers the individual to the VCL

(used in acute crises requiring emergency intervention or “rescue”); 2) researcher offers the participant a transfer to the VCL, but does not perform the transfer if he/she does not wish to be transferred (used in non-emergency situations).

Breach of Confidentiality. Statistical data files will be kept VINCI project servers maintained by VINCI OI&T personnel and only summarized data without protected health information (PHI) will be downloaded from VINCI to local storage media. Research staff will use an audited VINCI download utility to move summarized data for reports, presentations and publications from VINCI servers to local storage media. The VINCI download utility provides an audit path including a copy of the downloaded material. The data extraction tool will be adapted for use with software directly available on the VINCI platform (e.g. Microsoft Word and Excel) and study data will be stored and maintained on VINCI. All study team personnel with access to sensitive patient data will stay current on their VA approved information security training and VA approved privacy policy training.

Adverse Events (AE). AEs may include, but are not limited to: worsened physical or mental health, or inadvertent disclosure of confidential research information. Serious Adverse Events (SAE) may include: death, hospitalization due to worsening psychiatric symptoms or suicidal ideation, or all life threatening or disabling/incapacitating events among research participants. Per IRB regulations, SAEs, any event resulting in a deviation from the study protocol (e.g., emergency hospitalization to address suicidal behaviors) or death will be reported to the PI within 24 hours and to the IRB in 48 hours. This will be completed in order to assess significance and determine an appropriate response. AEs that involve temporary distress will be noted by interviewers and provided to the IRB in an annual report.

Confidentiality of Records: Numerous protections are in place to reduce the likelihood of loss of confidentiality. All research data will be kept in locked filing cabinets in secure areas, absent of identifying information, and coded by research number only. Files containing consent forms and other items with identifying information will also be kept in locked filing cabinets, but these will be separate from cabinets containing data from this study. All electronic files, including therapy notes, will be maintained on a secure study folder behind the VA firewall. Only approved study team personnel will be granted access to this data. All identifiable information will be stored in a separate folder behind the firewall from the de-identified study ID and data.

Potential Benefits of Research to Participants and Others. There may be direct and/or indirect benefits of study participation. Participants may initiate a psychosocial or other nonpharmacological pain treatment, or a related treatment that may help improve physical and/or mental well-being. Dissemination of the findings from the study will contribute to the extant literature and will inform future implementation efforts.

Importance of Knowledge to be Gained. Chronic pain conditions are among the most common and disabling in the United States and management of chronic pain with opioid analgesics increases risk of premature death. The latest Clinical Practice Guidelines detail utilization of nonpharmacological approaches, including psychosocial pain treatments as front-line treatment. Beliefs regarding the utility of such treatment often act as a barrier to patients initiating and engaging in such treatment. The proposed study is a one-session, cognitive-behavioral intervention that is delivered by phone targeting treatment initiation and engagement through reducing thoughts that act as barriers. Patients receiving such treatment may be more likely to initiate psychosocial and other nonpharmacological pain treatments that are safer alternatives to opioid analgesics. Additionally, there is less patient and provider burden to help

increase treatment initiation given it is one session and can be delivered by phone. Knowledge gleaned from this study will help inform future implementation and dissemination efforts.

Data Safety & Monitoring Plan

Data Safety. To ensure safety of participants in the study proposed and validity and integrity of data collected, the PI ([name]) will oversee all data and safety monitoring functions and the research team will be advised that he will be the primary contact overseeing these activities. The investigators will meet regularly to monitor study progress and discuss the implementation of monitoring procedures. The PI will also meet regularly with the research coordinator and staff to review monitoring procedures and ensure all efforts are being taken to minimize risks to participants. As indicated below, the PI will track all negative outcomes and incidents as well as conduct interim data analysis every 12 months after the study has started. The study design will be significantly modified if the study is creating potential harm to our participants.

The PI and [name] will regularly oversee all aspects of the study, including participant recruitment, informed consent, data collection, management, and analysis, as well as regularly assess the risk/benefit ratio associated with participation in the study. All research staff will participate in an intensive training to help them understand the importance of reducing the risk for participants and learning how to recognize and report any AE or SAE. SAEs may include: death, hospitalization due to worsening psychiatric symptoms or suicidal ideation, or all life threatening or disabling/incapacitating events among research participants. AEs may include, but are not limited to: physical injuries, worsened physical or mental health, or inadvertent disclosure of confidential research information.

If an SAE occurs, the PI will immediately contact the IRB, followed by a written report in 24 hours. He will make a decision whether there is sufficient evidence to suspend data collection, allow for further IRB review, modify the protocol, or make other changes to reduce potential risk to participants. The study will resume based on agreement of the PI, and an IRB member (the chair will recuse himself because he is a co-I on the study). Immediate evaluation will occur to determine if any extra steps can be taken to minimize the likelihood of that type of AE occurring again. If changes can be made, a report/amendment will be written and submitted to the IRB.

As part of a standard practice, the PI will supervise the implementation of one audit within 4 months after study recruitment and one regularly per year afterwards of the materials collected and produced as part of the study at each site to ensure proper confidentiality and compliance with ethical principles, including informed consents, questionnaire data, and to make sure that the research staff are following established protocols. The PI will provide an annual summary report of all AEs to the IRB as part of the annual review. If no adverse events have occurred, the report will state, "No adverse events affecting human participants have occurred during this project year."

Data Monitoring. To ensure adequate participant recruitment and enrollment, each week, the PI will discuss the current number of participants contacted, screened, and enrolled from each site and compare those numbers to the expected based on our preliminary data. If after the first 4 months, it appears we are not reaching our expected number of participants, the PI will discuss potential barriers/obstacles and solutions with the research team and we will enact contingency plans as needed.

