2.0 Introduction

Chronic pain is a significant public health problem. In the United States, the estimated annual cost burden of chronic pain on healthcare, disability, lost wages and productivity exceeds \$500 billion.¹ Low back pain, neck pain, and other musculoskeletal conditions are each among the leading contributors to disability.² Veterans are vulnerable to develop chronic pain¹ and report higher pain severity relative to the general population.³ Health record data from the Veterans Health Administration (VHA) indicate that 55% of almost 10 million Veterans in VHA care between 2000 and 2011 had a diagnosis of a musculoskeletal condition.⁴ Veterans with pain conditions report poorer psychosocial functioning, exhibit high rates of psychiatric and medical comorbidity, and are at increased risk of suicide.^{4,5}

Opioid misuse: A National Public Health Emergency. There is overwhelming evidence of premature mortality and other significant adverse outcomes associated with opioid analgesic use.⁶ There were nearly 50,000 opioid overdoses in the United States in 2019 representing greater than a 4-fold increase from 2002.⁷ Suicides involving opioids nearly tripled from 1999 to 2014.⁸ Studies among Veterans indicate that higher doses of opioid analgesics increase risk of suicide,⁹ and overdose risk is increased by over seven-fold with higher doses of opioid analgesics.¹⁰ Longitudinal studies indicate that long-term opioid analgesic use (i.e., greater than 90 days) is associated with depression onset and recurrence,^{11,12} the development of opioid use disorders, and aberrant drug-related behaviors (e.g., illicit substance use, alternative routes of administration)¹³ among individuals experiencing chronic pain.

Overall, the long-term use of opioid analgesics to manage chronic pain is guided by little evidence and is associated with increased morbidity and mortality. In most cases, safe and effective alternatives to opioid analgesics are preferred in managing chronic pain.^{14,15} Many non-pharmacological pain treatments have good evidence and are associated with lower risk and similar, if not greater, potential for improvement.¹⁶ There is a need to identify ways to engage Veterans in non-pharmacological pain treatment prior to the onset of the adverse outcomes of opioids, after the onset of adverse outcomes, or even prior to starting opioid analgesics to prevent the poorer prognosis associated with long-term opioid analgesic use.

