5.0 Study Procedures

5.1 Study Design

Study sample: We will recruit 300 veterans with chronic pain for this randomized clinical trial. Participants will be randomized to either the CBT-TS condition or an education control condition. Participants in both conditions will complete assessments on pain, treatment engagement, and opioid use at baseline, and 1-, 3-, and 6-months post-treatments to assess primary, secondary, and exploratory outcomes.

Screening: This study aims to recruit 300 eligible participants nationally. Potential participants with at least a 90-day supply of opioid analgesics will be identified through queries of VHA administrative data from the Corporate Data Warehouse. Potential participants will be mailed a personalized letter describing the study and provided with a toll-free number so that they can contact study staff if they are interested in participating as well as opt out of future contact. The project coordinator will call all patients who receive a letter unless the patients call a number to opt out. An advantage of our procedure is the ability to identify gender, race/ethnicity, and high-risk opioid use (e.g., high dose) to help target recruitment of these Veterans. We can accomplish this by sending out recruitment letters to a higher proportion of these groups relative to the overall proportion. Data extraction will occur monthly to identify Veterans who have newly initiated opioid therapy. To reach 300 total participants, we would need to start from a recruitment pool of less than ~5,000-10,000 people based on the following estimates: screened 95% of people, 75-90% ineligibility rate, and 25-60% declining the invitation to participate. Therefore, there is a large enough pool to reach our conservative screening estimate with large numbers of Veterans across demographic characteristics.

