5.5 Study Evaluations

Medical Record Review and Treatment Utilization Form (TUF). Treatment utilization will be assessed through medical record review. The measure can be found in the **Appendix**. CAPRI and Joint Longitudinal Viewer will be used to access medical records. These are used at every VAMC and regional office and are accessible from every VA site of care. We will abstract data related to treatment utilization and medications across VHA facilities, including types of service (e.g., CBT-CP, chiropractic care), dates of service, number of sessions, and type and dose of medications. Non-VA medications known to VA providers and non-VA treatment notes are also included in the medical record. This data will be abstracted as available. Treatment initiation of psychosocial pain treatment is defined as attending at least one session of CBT-CP, ACT, or MBSR. We will also utilize data extraction from the Corporate Data Warehouse (CDW) to initially capture treatment utilization from medical records to assist in the medical record review. CDW contains financial, enrollment, demographic, diagnostic, treatment utilization, and other data across Veterans from 1979 to present. For training of the medical record chart review, the research staff will code 12 charts unrelated to the study and then meet to discuss and resolve differences. During the review for the study, they will overlap on 10 charts to facilitate agreement and ongoing discussion of differences will be addressed as needed. Drs. [name] and [name] will make the final decisions.

We will also collect self-report data on non-VHA care not identified in the medical record. *Self-report data will be exploratory* to evaluate the extent to which treatment was utilized outside the VHA and will not be included in the analyses of the primary and secondary outcomes. Participants will be asked at baseline and each follow-up period whether they have initiated treatments and the number of sessions for each type of treatment they have attended since the previous assessment. We will ask participants to provide information about where the treatment was received, and type of treatment (e.g., CBT-CP, MBSR, chiropractic, acupuncture).

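### The plan names no source or schedule for finding serious adverse events and states no safety use for its record extraction, so deaths, overdoses and admissions in participants lost to contact may go undetected

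*Combined protocol and SAP*

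**What the plan says.** **Definition.** Section 6.0 gives the list twice. Under Adverse Events: "Serious Adverse Events (SAE) may include: death, hospitalization due to worsening psychiatric symptoms or suicidal ideation, or all life threatening or disabling/incapacitating events". Under the Data Safety & Monitoring Plan: "SAEs may include: death, hospitalization due to worsening psychiatric symptoms or suicidal ideation, or all life threatening or disabling/incapacitating events among research participants".

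**Detection.** The Adverse Events paragraph says "AEs that involve temporary distress will be noted by interviewers and provided to the IRB in an annual report". The Data Safety paragraph says that "the PI will track all negative outcomes and incidents as well as conduct interim data analysis every 12 months". Staff are trained to recognise and report events. The suicide-risk procedures under Protection Against Risk begin with what a participant says or scores during a contact.

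**Record data.** Section 5.5, on the Treatment Utilization Form (TUF), says "We will abstract data related to treatment utilization and medications across VHA facilities, including types of service (e.g., CBT-CP, chiropractic care), dates of service", together with session counts and the type and dose of medications. CDW extraction supports that review. The form itself is in an appendix that was not available.

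**Setting.** The Introduction states that "overdose risk is increased by over seven-fold with higher doses of opioid analgesics", and also cites suicide and premature death. The Abstract says that the funder did not require a data safety and monitoring board.

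**The concern.** A participant who has died, overdosed or been admitted may well be one who does not answer the follow-up call. If events surface only when someone tells the staff, the information is weakest where it matters most.

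The PI and the IRB are the safety oversight in this trial, and the PI has to judge whether the study is creating harm. Without a defined search, a low event count cannot separate events that did not occur from events that nobody heard of. The means of closing much of this gap are already in use for the trial's main outcomes, but nothing in the text directs them at safety.

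**Working it through.** **1. Detection routes described in section 6.0**
- Suicide-risk procedures: start from a participant's statement or answers during a contact.
- Interviewers: note events, but the sentence covers temporary distress only.
- Staff training: helps once an event has come to notice; no source is named.
- PI tracking of negative outcomes: refers the reader to the text below it, which gives no source, schedule or procedure for unreachable participants.
- Audits: cover consents, questionnaire data and adherence to procedures.
- Data Monitoring paragraph: covers recruitment and enrolment numbers.

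None of these names a source independent of contact. The PI tracking sentence does not exclude one. Scheduled contacts after the session are at 1, 3 and 6 months (section 5.1).

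**2. Record data and questionnaires (section 5.5)**
- The stated abstraction is treatment utilisation and medications. Table 5 adds other treatments and non-opioid analgesics. Deaths, admissions, emergency visits and overdoses are not listed.
- CDW is described as holding diagnostic data, among other types, so a safety query looks feasible.
- The ORBQ records risk behaviours, not overdose events. Item 5 of the Paykel scale asks about a suicide attempt since the last visit, but only in a completed assessment.
- The Missing Data paragraph of section 5.7 treats discontinuation as missing data. It has no step to establish whether a lost participant has died or been admitted.

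**3. Coverage of the serious-event list**

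| Event | Named as serious? |
|---|---|
| Death | Yes |
| Life-threatening overdose | Yes, as a life-threatening event |
| Admission for psychiatric or suicidal cause | Yes |
| Admission for overdose or other medical cause | Only if life threatening or disabling |
| Suicide attempt without admission | Only if life threatening or disabling |

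For the first two rows the gap is one of finding the event. For the last two it is also one of definition.

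**4. How many participants could be out of contact**

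Input: the power paragraph of section 5.7 increases 250 by 20% for attrition.
- 250 × 1.20 = 300, which reproduces the plan's figure.
- 300 − 250 = 50, and 50/300 = 16.7%.

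Taking 20% of 300 instead would give 60, but the plan's wording supports 50.

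**5. Illustration only.** The documents give no event rate, so a six-month risk r is assumed. With 50 participants unobserved throughout, the expected number of events is 50 × r and the chance of at least one is 1 − (1 − r)^50.

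| Assumed r | Expected events | Chance of at least one |
|---|---|---|
| 1% | 0.5 | 40% |
| 2% | 1.0 | 64% |
| 5% | 2.5 | 92% |
| 10% | 5.0 | above 99% |

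At any given r these figures lean high. Someone lost at month 6 may have been reached at months 1 and 3, and losing contact does not end access to the record.

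**6. Reporting clocks.** The Adverse Events paragraph has serious events reported to the PI within 24 hours and to the IRB in 48 hours. The monitoring plan has the PI contact the IRB at once, with a written report in 24 hours. The two do not agree.

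**The case against.** The strongest reply is that the plan is silent rather than restrictive. No sentence limits detection to participant contact. The PI is to track all negative outcomes, and the staff trained to report events include those who read charts. Section 5.2 already uses the medical record to update contact details. The abstraction list is introduced as examples, and the form's fields could not be checked. All of this stands. A reader might infer that serious events are learned of only through contact and are therefore missed; the documents support only that they may be.

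The definition is also wider than its hospitalisation clause suggests. The list is open. Events causing a protocol deviation go on the same clock, with emergency admission for suicidal behaviour as the example. Worsened physical or mental health is a reportable adverse event, and endorsed suicidality triggers a full risk assessment. That stands too, but it helps only once an event is known.

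Three further inferences do not hold:
- **A fixed share of events is lost.** Any such percentage needs event rates that the documents do not give. At equal risk it merely restates the attrition allowance.
- **The annual report could truthfully say "No adverse events affecting human participants have occurred during this project year".** That sentence is for a year with no adverse event of any kind. Any event seen among contacted participants rules it out: at an assumed 5%, 250 × 0.05 = 12.5 would be expected over follow-up.
- **A monthly safety query already exists in all but name.** Section 5.1 says "Data extraction will occur monthly to identify Veterans who have newly initiated opioid therapy"; that is a recruitment query, not a search of enrolled participants.

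Finally, the intervention is a single session described as minimal risk, and no aim is a safety comparison. Unequal detection between arms is possible but speculative. This limits the weight of the point. It does not remove the need for a defined search in a population whose hazards the Introduction stresses.

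**Conclusion.** The point holds as a gap in safety ascertainment. The plan states no source or schedule for finding serious events, the routes it describes depend on staff hearing of them, and the record extraction has no stated safety use. Non-psychiatric admission is not named as serious in its own right. As written, the plan can be followed in full while a death, overdose or admission in an unreached participant goes unseen.

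About 50 of 300 participants could be affected, taking the attrition allowance as a proxy for being out of contact. The number of events cannot be derived from the documents. The conclusion assumes that the unseen form does not already hold these fields; if it does, what remains is to state their safety use, set a schedule and widen the list. The primary analysis and sample size are unaffected. The change is worth making because it is cheap and the data source is already in use.

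**What to change.** - **Extraction (section 5.5).** For all randomised participants through month 6, add date of death, any inpatient admission, any emergency visit, and any overdose or suicide-attempt entry to the TUF/CDW extraction. Run it at least at the 1-, 3- and 6-month time points, whether or not the participant was reached. Confirm which of these fields the form and CDW already supply, and say what applies after withdrawal of consent.
- **Definition (section 6.0, both places).** Add any hospitalisation, any overdose and any suicide attempt, including a positive Paykel item 5.
- **Reporting.** Tabulate record-based events by arm in the final report, with contact-reported events as a supplement. State in section 6.0 that this extraction is the source for the PI's tracking.
- **Reconcile** the two IRB reporting clocks in section 6.0.

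Cost: a few fields, one scheduled query of enrolled participants and an amendment to the adverse-event text. More events will have to be logged and reported, most of them unrelated to the session. Events outside the VA will still be captured only as available, so the search narrows the gap without closing it.
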